
To evaluate the efficacy of savolitinib plus osimertinib in patients who cross-over after progression on savolitinib plus placebo. ^a
	
 • Objective response rate is defined as the proportion of patients with measurable disease who have a CR or PR as determined by the investigator at the local site per RECIST 1.1. • Progression-free survival is defined as time from the first dose in the cross-over period until progression per RECIST 1.1 as assessed by the investigator or death due to any cause. • Duration of response is defined as the time from the date of first documented response during the cross-over period until date of documented progression per RECIST 1.1 as assessed by the investigator or death in the absence of disease progression. • Tumour size assessment is defined as the percentage change from baseline in TLs at 12 weeks per RECIST 1.1 as assessed by the investigator.

To evaluate the PK of savolitinib and osimertinib.
	
Plasma concentrations of savolitinib, osimertinib, and their metabolites.

To determine the prevalence of ctDNA clearance after savolitinib plus osimertinib or savolitinib plus placebo treatment in this patient population.
	
Total clearance in EGFR mutations at 6-weeks after therapy initiation (percentage and absolute change from baseline in EGFR mutation allele frequencies).

Safety objective:
	
Safety endpoints/variables:

To evaluate the safety and tolerability of savolitinib plus osimertinib or savolitinib plus placebo.
	
Safety and tolerability will be evaluated in terms of AEs, SAEs and discontinuation rate due to AEs. Clinical chemistry/haematology including LFTs, ECHOs, ECGs and vital signs including blood pressure and heart rate.

Tertiary/exploratory objectives:
	
Tertiary/exploratory endpoints/variables:

^a Baseline for ORR, PFS, DoR and tumour size assessments of patients who cross-over to savolitinib plus osimertinib from savolitinib plus placebo will be the progression scan on savolitinib plus placebo acquired within 28 days of the start of treatment in the cross-over period.

CCI

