In general, for efficacy endpoints the last observed measurement prior to randomisation will be considered the baseline measurement. However, if an evaluable assessment is only available after randomisation but before the first dose of randomised treatment then this assessment will be used as baseline. For safety endpoints the last observation before the first dose of study treatment will be considered the baseline measurement unless otherwise specified. For assessments on the day of first dose where time is not captured, a nominal pre-dose indicator, if available, will serve as sufficient evidence that the assessment occurred prior to first dose.

Assessments on the day of the first dose where neither time nor a nominal pre-dose indicator are captured will be considered prior to the first dose if such procedures are required by the protocol to be conducted before the first dose.

In all summaries change from baseline variables will be calculated as the post-treatment value minus the value at baseline. The percentage change from baseline will be calculated as $(\text{post-baseline value} - \text{baseline value}) / \text{baseline value} \times 100$. For any variable subjected to log transformation, the change from baseline calculated and summarised on the log scale will be back-transformed and presented as a ‘baseline scaled ratio’ (BSR). Percentage change will then be calculated as $(\text{BSR} - 1) \times 100$.

Efficacy data will be summarised and analysed based upon the FAS. Safety and treatment exposure data will be summarised based upon the safety analysis set. Study population and demography data will be summarised based upon the FAS. PK data will be summarised based upon the PK analysis set. Summaries will be repeated for the cross-over analysis set as applicable.

The stratification in the statistical analyses will be based on the values entered in the interactive web response system (IWRS) at randomisation, even if it is subsequently discovered that these values were incorrect.

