- Baseline for safety assessments will generally be the last value obtained prior to the first dose of study medication). Alternatively, if two visits are equally eligible to assess patient status at baseline (e.g., screening and baseline assessments both on the same date prior to first dose with no washout or other intervention in the screening period), the average can be taken as a baseline value. For non-numeric laboratory tests (i.e. some of the urinalysis parameters) where taking an average is not possible then the best value would be taken as baseline as this is the most conservative. In the scenario where there are two assessments on day 1, one with time recorded and the other without time recorded, the one with time recorded would be selected as baseline. Where safety data are summarised over time, study day will be calculated in relation to date of first treatment.
- Per Section 9.4.3 of the CSP, adverse events occurring in the savolitinib in combination with placebo group will be split into two presentations based on whether they occurred before or after cross-over.

Missing safety data will generally not be imputed. However, safety assessment values of the form of “< x” (i.e. below the lower limit of quantification) or > x (i.e. above the upper limit of quantification) will be imputed as “x” in the calculation of summary statistics but displayed as “< x” or “> x” in the listings. Additionally, adverse events that have missing causality (after data querying) will be assumed to be related to study drug.

Furthermore:

- For missing diagnostic dates, if day and/or month are missing, use 01 and/or Jan. If year is missing, put the complete date to missing.
- For missing AE start dates, the following will be applied:
 - a. Missing day: impute the 1st of the month unless month is the same as month of the first dose of study drug then impute first dose date
 - b. Missing day and month: impute 1st January unless year is the same as first dose date then impute first dose date
 - c. Completely missing: impute first dose date unless the end date suggests it could have started prior to this in which case impute the 1st January of the same year as the end date

When imputing a start date ensure that the new imputed date is sensible e.g. is prior to the end date of the AE.

- For missing AE end dates, the following will be applied:

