4.2.10 Analyses for cross-over patients

The assessment schedule for patients who cross-over will be determined by the point of cross-over, as described in Section 3.1.

Selected analyses will be repeated for the cross-over analysis set, including baseline characteristics, efficacy endpoints and safety analyses where sufficient data allow.

Any AE summary tables for cross-over patients will include all AEs that occurred after the start of cross-over treatment up until the end of the 28-day follow-up period. The 28-day follow-up period will be defined as the 28 days following discontinuation of treatment.

Cross-over analyses will not be presented by biomarker group.

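### Laboratory, vital-sign, ECG and LVEF summaries in the cross-over set have no cross-over baseline or Day 1, so by default they mix change on savolitinib plus placebo with change on the combination

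*SAP*

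**What the plan says.** For safety endpoints, SAP 4.1 states: "For safety endpoints the last observation before the first dose of study treatment will be considered the baseline measurement unless otherwise specified". SAP 4.2.5.1 repeats the rule ("Baseline for safety assessments will generally be the last value obtained prior to the first dose of study medication") and sets the clock: "Where safety data are summarised over time, study day will be calculated in relation to date of first treatment". The same section gives example visit windows for vital signs, keeps one value per patient per window (the one closest to the nominal day), and lets extreme-value summaries use every post-baseline or on-treatment value, whichever window it falls in.

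These analyses are then carried over to the cross-over analysis set. SAP 4.1: "Summaries will be repeated for the cross-over analysis set as applicable". SAP 4.2.10: "Selected analyses will be repeated for the cross-over analysis set, including baseline characteristics, efficacy endpoints and safety analyses where sufficient data allow". Table 2 also assigns safety data to that set.

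Other data are re-anchored at cross-over. A footnote to Table 1 sets a new scan baseline ("Baseline for ORR, PFS, DoR and tumour size assessments of patients who cross-over"), and Section 3.1 applies it to patients who cross over on objective progression. Table 1 times cross-over PFS from the first cross-over dose. For adverse events, 4.2.10 says: "Any AE summary tables for cross-over patients will include all AEs that occurred after the start of cross-over treatment".

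**The concern.** A table for the cross-over set should describe what happens on savolitinib plus osimertinib. With a baseline taken before any study treatment, a laboratory shift, QTcF increase or LVEF fall that arose on savolitinib plus placebo appears in that table as if it belonged to the combination. A patient who entered cross-over with an already abnormal value and then improved can still show as worsened. With no period limit, the worst value shown for the patient may date from before the second drug was added. With days counted from first treatment, a visit column has no common meaning in terms of time on the combination.

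**Working it through.** **Rules side by side, for the cross-over set**

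| Data | Baseline or start stated for cross-over? | Where |
|---|---|---|
| RECIST endpoints, crossing over on progression | Yes, the progression scan | Table 1 footnote, 3.1 |
| RECIST endpoints, crossing over without progression | Yes, initial randomisation kept explicitly | 3.1 |
| PFS | Yes, first cross-over dose | Table 1 |
| AE tables | Yes, start of cross-over treatment | 4.2.10 |
| Laboratory, vital signs, ECG, LVEF | No, so the general rules of 4.1 and 4.2.5.1 apply | none |

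Section 4.2.10 points to 3.1 for the cross-over assessment schedule, but 3.1 deals only with tumour assessments.

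**Baseline.** Under the general rule, reported change = (value on the combination − value before cross-over) + (value before cross-over − value before first dose). Only the first term arises after cross-over. With assumed QTcF values of 410 ms before first dose, 440 ms before cross-over and 445 ms after, the table reports 445 − 410 = +35 ms, of which 445 − 440 = 5 ms arose after cross-over. These values only illustrate the mechanism; the SAP gives no data on its size.

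**Reproducing the printed windows.** The rule in 4.2.5.1 puts the upper limit halfway between visits, reduced when an even number of days lies between them. Days 8 and 15 have 6 days between them, giving an upper limit of 11. Days 29 and 57 have 27 days between them, giving (29 + 57)/2 = 43. Applied throughout, the rule returns all seven printed windows: 2–11, 12–18, 19–25, 26–43, 44–71, 72–99 and 100–127. From Day 57 on, each is 28 days wide. Extending by 28-day visits gives Day 141 = 128–155 and Day 169 = 156–183.

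**Mapping cross-over visits.** Assume visits at relative Days 8, 15, 22 and 29. Study day = cross-over start day + relative day − 1.

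- Start on Day 85: study Days 92 and 99 fall in the Day 85 window, and 106 and 113 in the Day 113 window. A reading on the start day itself (Day 85) would be on the nominal day and would be the value summarised for that window.
- Start on Day 150: study Days 157, 164, 171 and 178 all fall in 156–183. Their distances from 169 are 12, 5, 2 and 9, so only Day 171 is summarised.

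For start days 44 to 295 (nine full 28-day cycles), the four visits span 29 − 8 = 21 days. They fit in one window for (28 − 21)/28 = 25% of start days and straddle two for the other 75%. At most two of the four readings therefore reach the by-visit table. Counted from the first cross-over dose, Days 8, 15, 22 and 29 each have their own window.

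**Pooling.** The Day 169 window (156–183) covers relative Days 72–99 for a patient who crossed over on Day 85 (156 − 85 + 1 = 72; 183 − 85 + 1 = 99), and relative Days 7–34 for one who crossed over on Day 150. One column would average both.

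**The case against.** The strongest reply is that the SAP nowhere says the cross-over tables use the pre-treatment baseline. That follows from silence, and the wording is hedged: the baseline rule holds only generally and unless specified otherwise, and repeats are selective and as applicable. The date of first treatment is not defined for a cross-over table. This stands as a description of the text, but it does not remove the problem. No exception is specified, so the default governs; and if the date can be read two ways, two programmers can produce different tables.

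Several stronger readings are tempting, but the SAP does not support them:

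- **A pre-randomisation baseline.** That rule in 4.1 is for efficacy; the safety baseline is the last value before first dose.
- **All cross-over safety output is affected.** AE tables are already anchored at the start of cross-over treatment, and 4.2.5.1 splits placebo-arm AEs into before and after cross-over.
- **All first-month visits collapse into one window.** Under the assumed schedule this holds for 25% of start days. The actual schedule is in the protocol's Table 2, and the printed windows are an example for vital signs.
- **Early readings are lost.** They leave only the by-visit tables. Extreme-value summaries use all post-baseline values and listings show every contributing value. LVEF is summarised at baseline and end of treatment, so windows do not touch it.

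It is also fair that change from an untreated baseline is a legitimate display of cumulative toxicity, that 3.1 deliberately keeps the initial baseline for some cross-over patients' scans, and that these analyses are descriptive in a subset of one arm of a trial that stopped recruiting early. This argues for keeping the pre-treatment comparison as an addition and limits the weight of the point.

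**Conclusion.** The point holds for non-AE safety data in the cross-over analysis set. The SAP states one baseline and one day origin, repeats the analyses in that set, and specifies no exception. Followed as written, change-from-baseline, shift and QTcF-increase results there carry over change from savolitinib plus placebo, and extremes can come from before cross-over.

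The size of the carried-over change cannot be derived from the SAP. The merging of visits can be derived, but only under the assumed visit days: one or two 28-day windows instead of four separate ones, for cross-over on Day 44 or later. No inferential result is affected. It should be corrected because these tables are planned output and would otherwise misattribute change to the combination.

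**What to change.** Add a paragraph to SAP 4.2.10 stating that, for laboratory, vital-sign, ECG and LVEF summaries in the cross-over analysis set:

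- baseline is the last value before the first cross-over dose;
- study day and visit windows count from that dose;
- by-visit and extreme-value summaries use only values from that dose to 28 days after the last dose.

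Change from the pre-treatment baseline may be shown in addition, labelled as such.

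The cost is one paragraph and a second baseline/period flag in the safety datasets. The drawback is that patients with no assessment shortly before cross-over will use their last monotherapy value, possibly some time old, as baseline.

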4.2.5.2 Adverse events (AEs)

Adverse events will be coded using the most recent version of MedDRA that have been released for execution at AstraZeneca. Adverse events will be graded according to the National Cancer Institute CTCAE (Version 5.0).

Summary information (the number and percent of patients per treatment group) by system organ class and preferred term will be tabulated for savolitinib plus placebo and savolitinib plus osimertinib for:

- All AEs
- All AEs possibly related to study medication (as determined by the reporting investigator)
- AEs with maximum reported CTCAE grade
- AEs with CTCAE grade 3 or higher
- AEs with CTCAE grade 3 or higher, possibly related to study medication (as determined by the reporting investigator)
- Most common AEs (occurring in at least 10% of patients)
- Most common non-serious AEs (occurring in at least 5% of patients)
- AEs with outcome of death
- AEs with outcome of death possibly related to study medication (as determined by the reporting investigator)
- All SAEs
- All SAEs possibly related to study medication (as determined by the reporting investigator)

- AEs leading to discontinuation of study medication
- AEs leading to discontinuation of study medication, possibly related to study medication (as determined by the reporting investigator)
- AEs leading to dose reduction of study medication
- AEs leading to dose reduction of study medication, possibly related to study medication (as determined by the reporting investigator)
- AEs leading to dose interruption of study medication
- AEs leading to dose interruption of study medication, possibly related to study medication (as determined by the reporting investigator).

AEs with outcome of death, SAEs, AEs leading to discontinuation of each treatment and AEs possibly related to treatment will be listed.

Any AE occurring before the first dose of study intervention will be included in the data listings but will not be included in the summary tables of AEs. Adverse event summary tables will include only treatment-emergent AEs. The following events are considered treatment emergent:

- Adverse events with an onset date on or after the first dose of randomised study intervention and within the safety follow-up period (28 days [\pm 7 days] after last dose of all study intervention). Any events in this period that occur after a patient has received further therapy for cancer (following discontinuation of all study intervention) will be flagged in the data listings.
- Worsening of pre-existing events on or after the first dose of study intervention and within the safety follow-up period.

Any events in this period that occur after a patient has received further therapy for cancer (following discontinuation of all study intervention) will be flagged in the data listings, but not included in the summaries.

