1.2 Study Design

This is a multi-centre, Phase II, double-blind, randomised study designed to determine the efficacy of savolitinib administered orally in combination with osimertinib versus savolitinib in combination with placebo in patients with EGFRm+, MET amplified, locally advanced or metastatic NSCLC who have progressed on previous osimertinib treatment.

Prior to CSP Version 3.0, approximately 56 patients were planned to be randomised in a ratio of 1:1 to receive treatment with CCI savolitinib once daily plus CCI osimertinib once daily, or CCI savolitinib once daily plus placebo. At least half of the patients randomised into the study will be second line patients who were treated with osimertinib as first line therapy. Randomisation will be stratified according to the number of prior lines of therapy (i.e., osimertinib monotherapy as first line or \geq second line [which includes patients who received osimertinib monotherapy before or after chemotherapy]).

Prospective testing of tumour specimens to determine MET amplification by central fluorescence in situ hybridisation (FISH) using tumour specimens collected after progression on prior treatment with osimertinib should be performed at Pre-screening in advance of Screening. Patients determined to be MET amplified in Pre-screening will undergo screening during the 28 days prior to randomisation to confirm eligibility.

All patients confirmed as eligible will begin treatment on Day 1 with savolitinib plus osimertinib or savolitinib plus placebo. Treatment will continue once daily in 28-day cycles until either

objective PD by RECIST 1.1 is assessed, unacceptable toxicity occurs, consent is withdrawn, or another discontinuation criterion is met. Patients randomised to the savolitinib plus placebo arm may cross-over to open-label savolitinib plus osimertinib following investigator-assessed objective PD to ensure that all patients enrolled may have the opportunity to receive the combination of savolitinib plus osimertinib.

A non-comparative interim futility analysis for the savolitinib plus placebo arm was planned to occur after 20 patients overall (10 per arm) had the opportunity of being treated for 2 RECIST post-baseline scans (12 weeks). Recruitment was to continue during this interim futility analysis.

[figure not shown]
Randomised study design, cross-over study design and end of study design are described in the CSP Section 4.1.

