Under CSP V3.0, as a result of AstraZeneca's decision to terminate study recruitment early, the planned interim futility analysis and primary analysis will not be performed, and there will be no requirement for data review by the IDMC. Alternatively, an initial data cut-off (DCO) will occur following the early termination of study recruitment to allow an early review of the data by AstraZeneca. The study will be unblinded after completion of data cleaning activities on the initial DCO data, and patients on savolitinib monotherapy (savolitinib plus placebo) will be given the opportunity to cross-over to the savolitinib plus osimertinib arm after approval by AstraZeneca.

If it is decided that a patient will switch to savolitinib plus osimertinib before final database lock, then they will follow the scheduled procedures described in CSP Table 2. Patients may otherwise choose to remain on savolitinib monotherapy (as long as, in the opinion of the investigator, they are still receiving clinical benefit and have not reported PD). All patients will be followed until the final DCO for the final analysis, which will occur after all randomised patients have had a 9-month follow-up. CCI

For an overview of the study design see [Figure 1](#).

Figure 1 Study Design

EGFRm+ = Epidermal growth factor receptor mutation positive; MET = Hepatocyte growth factor receptor; NSCLC = Non-small cell lung cancer.

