3.3 Safety Variables

3.3.1 Exposure and dose interruptions

Exposure (i.e. duration of treatment) will be defined for both savolitinib and osimertinib/placebo as follows:

Total (or intended) exposure of study treatment

- Total (or intended) exposure = $\min(\text{last dose date where dose} > 0 \text{ mg, date of death, date of DCO}) - \text{first dose date} + 1$

Actual exposure of study treatment

- Actual exposure = intended exposure – total duration of dose interruptions, where intended exposure will be calculated as above, and a dose interruption is defined as any length of time where the patient has not taken any of the planned daily dose.

The actual exposure calculation makes no adjustment for any dose reductions that may have occurred.

Number of treatment cycles received

Exposure will also be measured by the number of cycles received. A cycle corresponds to a period of 28 days. If a cycle is prolonged due to toxicity, this should still be counted as one cycle. A cycle will be counted if treatment is started even if the full dose is not delivered.

Missed or forgotten doses

Missed and forgotten doses should be recorded on the DOSE module as a dose interruption with the reason recorded as “Subject forgot to take dose”. These missed or forgotten doses will not be included as dose interruptions in the summary tables, but the information will appear in the listing for dosing. However, these missed and forgotten doses will be considered in the derivation of actual exposure.

Patients who permanently discontinue during a dose interruption

If a patient permanently discontinues study treatment during a dose interruption, then the date of last administration of study medication recorded on DOSDISC will be used in the programming.

Safety follow-up

- Total Safety Follow-up = $\min(\text{last dose date} + 28 \text{ days}, \text{date of withdrawal of consent}, \text{date of death}, \text{date of DCO}) - \text{first dose date} + 1$

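### Monotherapy AE windows close at cross-over, but AEs are tabulated only as crude percentages and the exposure formulas make no matching cut

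*SAP*

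**What the plan says.** - **Measure.** SAP Section 4.2.5.2: "Summary information (the number and percent of patients per treatment group) by system organ class and preferred term will be tabulated" for the two arms. Section 4.2.5.3 does the same for AEs of special interest. Section 4 has no AE rate per time at risk, time-to-first-AE summary or common-window table.
- **Split at cross-over.** Section 4.2.5.1 says that AEs in the savolitinib plus placebo group "will be split into two presentations based on whether they occurred before or after cross-over". Section 4.2.10 completes this from the other side: "Any AE summary tables for cross-over patients will include all AEs that occurred after the start of cross-over treatment".
- **Who can cross.** Only the placebo arm. Section 1.2 allows it after progression ("Patients randomised to the savolitinib plus placebo arm may cross-over to open-label savolitinib plus osimertinib following investigator-assessed objective PD") and, under CSP V3.0, after unblinding ("will be given the opportunity to cross-over to the savolitinib plus osimertinib arm after approval by AstraZeneca"). Section 3.1 provides for patients who cross after unblinding without having progressed. Cross-over is optional: "Patients may otherwise choose to remain on savolitinib monotherapy".
- **End of AE collection.** In both arms, 28 days after the last dose (Sections 3.3.3 and 4.2.5.2). The final data cut-off (DCO) is 9 months after the last randomisation (Section 4.2.4).
- **Exposure.** Section 3.3.1 ends total exposure at last dose, death or DCO. "Total Safety Follow-up" ends at last dose plus 28 days, consent withdrawal, death or DCO. Neither formula names cross-over. Section 4.2.5.8 summarises exposure. Nothing in Section 4 uses the follow-up variable.

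**The concern.** A crude percentage depends on how long each patient is observed. Here the design can shorten that time in one arm only. A placebo-arm patient who crosses stops contributing monotherapy AEs on the day cross-over treatment starts, and also loses the 28-day tail that other patients keep. A combination patient in the same clinical position stays in the table.

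Safety and tolerability of both regimens is a stated objective (Section 1.1), and the AE tables show the arms side by side. A reader who takes the difference in percentages at face value would credit part of a difference in observation time to the addition of osimertinib.

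The usual safeguard is to look at exposure, and it may fail here. Savolitinib continues through cross-over, so the placebo arm's savolitinib exposure, computed as Section 3.3.1 is written, may include time on the combination. The AE count would stop at cross-over while the exposure figure ran on.

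**Working it through.** The SAP states no AE rate, exposure time or safety precision, so there is no figure of its own to reproduce. The check asks what the cut does when the true AE hazard is the same in both arms.

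**Inputs**

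| Input | Value | Source |
|---|---|---|
| Final DCO | 9 months after last randomisation | SAP 4.2.4 |
| Cross-over at unblinding | placebo arm only, optional | SAP 1.2 |
| Accrual | uniform over 12 months (also 6 and 18) | assumption |
| Unblinding | 1 or 3 months after last randomisation | assumption |
| Treatment duration | exponential, median 6 months, both arms | assumption |
| AE hazard h | 0.10 per month, both arms | assumption |

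**Formula.** Let λ = ln 2 / 6 = 0.1155 per month. If calendar limits cap the window at L months, the chance of an AE while observed is h/(h+λ) × [1 − exp(−(h+λ)L)]. A patient randomised s months before the last one has L = s + 9 on the combination, or L = s + u on monotherapy if crossing at unblinding (u = 1 or 3). Averaging over s from 0 to 12, with a = 9 or u:

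P(a) = h/(h+λ) × {1 − exp(−(h+λ)a) × [1 − exp(−12(h+λ))] / [12(h+λ)]}

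Here h+λ = 0.2155, h/(h+λ) = 0.464 and the last fraction is 0.3575.

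- Combination, a = 9: 0.464 × (1 − 0.1438 × 0.3575) = 44.0%.
- Monotherapy, a = 1: 0.464 × (1 − 0.8061 × 0.3575) = 33.0%, a gap of 11.0 points.
- Monotherapy, a = 3: 0.464 × (1 − 0.5238 × 0.3575) = 37.7%, a gap of 6.3 points.

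Mean observed time is 7.0 months against 4.5 to 5.3. If half of the ongoing monotherapy patients cross, the gap halves to about 3 to 5.5 points. If none cross, it is zero.

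**Sensitivity (simulation)**

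- Adding the 28-day tail for patients who do not cross gives a gap of 7 to 12 points, so leaving it out above did not create the effect.
- With full crossing and no tail, 6-month accrual gives 10 to 17 points and 18-month accrual about 4 to 8.
- With 18-month accrual, unblinding at 3 months and the tail included, 70% crossing at progression alone gives 46.1% against 49.2%. If all the rest also cross at unblinding, it is 41.5% against 49.3%.
- With a front-loaded hazard (0.40 in month 1, then 0.03 per month; 12-month accrual, full crossing, tail included), crude incidence is 44.6% against 40.2 to 41.9%, a gap of 3 to 4 points.
- If combination treatment is shorter (median 4 months against 6; 18-month accrual, unblinding at 3 months, 70% crossing at progression and 50% at unblinding), the result is 41.4% on the combination against 43.8% on monotherapy. The sign reverses.

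**Does a rate repair it?** Patients with an event divided by time at risk to first event, with monotherapy time cut at cross-over, is equal in both arms in every constant-hazard scenario. Under the front-loaded hazard it is not: 114 per 100 patient-years on the combination against 133 to 149 on monotherapy, an artificial excess of 17 to 31% (133/114 and 149/114).

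**The case against.** The case against has weight on several points.

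- A reader might infer that the combination arm is always followed to the final cut-off and monotherapy never beyond cross-over. The SAP does not say so. Both arms stop 28 days after last dose, only patients still on treatment reach the DCO, and only patients who cross lose window.
- A reader might infer that the bias always runs against the combination. The cut can only lower monotherapy incidence, but the net gap also depends on treatment duration and can reverse.
- A reader might credit a large gap to cross-over when monotherapy patients simply progress sooner. With medians of 3 and 6 months (12-month accrual, unblinding at 3 months, no tail), crude incidence is 27.4% against 44.0%, but it is already 29.8% with no crossing at unblinding. Cross-over explains 29.8 − 27.4 = 2.4 of the 16.6 points.
- Safety is descriptive. Section 2.1 says that it is not formally analysed, and the safety objective does not set one regimen against the other. No formal safety comparison is being biased. Percentages over unequal windows can still mislead when shown side by side.
- Crude treatment-emergent tables are conventional, the split at cross-over is needed for attribution, and exposure is shown separately. This last defence is weakened because Section 3.3.1 does not cut exposure at cross-over.
- Rates per patient-year are no cure on their own, as the front-loaded example shows. This stands and shapes the fix.

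**Conclusion.** The concern holds in a limited form. For placebo-arm patients who cross, the monotherapy AE window closes at the start of cross-over treatment, no AE summary accounts for time at risk, and the exposure and follow-up formulas make no matching cut. With equal hazards and equal treatment durations, the cut alone lowers monotherapy crude incidence by about 6 to 11 points if all ongoing patients cross at unblinding, and by about 3 to 5.5 points if half do.

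These sizes rest on assumed accrual, unblinding date, treatment duration, hazard and uptake, none of which the SAP gives. The gap is smaller for early-onset AEs, and its net direction is not guaranteed. The point should be addressed as a matter of sound description. It does not invalidate a planned test.

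**What to change.** 1. In Section 3.3.1, for the randomised-period summaries of savolitinib plus placebo, end exposure and Total Safety Follow-up at the first cross-over dose. Report cross-over exposure separately.
2. Keep the crude tables and show time at risk beside each, computed on the same window as the AE count.
3. For all AEs, grade 3 or higher, SAEs, AEs leading to discontinuation and AEs of special interest, add time to first event as a cumulative incidence by arm. Censor at the first cross-over dose, end of safety follow-up or DCO, with death as a competing event. Exposure-adjusted rates can supplement this.
4. State that between-arm remarks will not rest on the rates alone, because they assume a constant hazard.

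The cost is SAP wording and a few descriptive tables, using dates that the listed derivations already need. Estimates will be imprecise in a trial that stopped recruiting early. Censoring at a cross-over triggered by progression also assumes that AE risk is not tied to progression, which the report should say.
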